1.9 Interviews, Focus Groups, Surveys, and/or Observations

N/A

B. Study Instruments

- **Evaluation Instrument Details – see above. The case report forms are Figures 3 & 4**

2.2 Research Staff Training – N/A

2.3 Research Sites

The Valley Hospital & Intuitive Surgical Training Center, Atlanta, GA

3.0 Multi Center Research N/A

4.0 Research Data Source/s

4.1 Subject Selection and Enrollment Considerations

A. Method to Identify Potential Subjects

For the non-robotic surgeons, we will use any Board Certified surgeons on staff at The Valley Hospital. For the robotic surgeons, we will use any The Valley Hospital surgeons with unrestricted robotic privileges or any similarly credentialed robotic surgeons we encounter at the Intuitive Surgical Training Center.

B. Recruitment Details –

[name] will approach surgeons to ask for their participation and guide them through the study process

C. Subject Screening –

Surgeons will review the below criteria and self-select whether they are eligible

- **Inclusion Criteria –**
Group A (35 surgeons) Board Certified surgeons
Group B (18 surgeons) Board Certified surgeons with unrestricted robotic privileges
- **Exclusion Criteria –** Surgeons unwilling to spend adequate time to participate in the study or those who are not Board Certified

4.2 Secondary Subjects

N/A

4.3 Number of Subjects

A. Total Number of Subjects

53

4.4 Consent Procedures

A. Consent Process

- **Location of Consent Process**
In lieu of signing traditional informed consent, each surgeon will be provided with a Study Information Sheet. Their participation in the study will serve as implied informed consent.
- **Consent Discussion Duration**
5 minutes or less
- **Coercion or Undue Influence**
N/A
- **Subject Understanding**
Their participation will imply their understanding

B. Waiver or Alteration of Consent Process

▪ **Waiver or Alteration Details**

This study does not involve any patient care or any other risky situations. In fact, this study carries the smallest possible risks to the study subjects. At the same time, the surgeons who agree to be subjects are very busy people. Keeping the enrollment process to a minimum will be critical for obtaining participation.

- **Destruction of Identifiers**
No Identifiers will be collected (see Figure 3)
- **Use of Deception/Concealment**
N/A
 - a. **Minimal Risk Justification**
No patient care of any kind will be included in the study. The only study activity will be manipulation of inanimate objects.
 - b. **Alternatives**
Use of human or animal tissue is not practical, because the study design calls for uniformity of the model objects. The materials within the balloons are similar to fluids that are present during surgical dissection.
 - c. **Subject Debriefing**
Each surgeon will be told whether or not they ordered the balloons correctly right after they do so, and they will be asked to keep this information to themselves.

C. Documentation of Consent

- **Documenting Consent**
N/A
- **Waiver of Documentation of Consent (i.e., will not obtain subject's signature)**
Each subject will receive a Study Information Sheet

B. Removing a Subject

If a subject decides to cease participation we will shred their forms and choose a subsequent study subject.

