1.3 Research Design and Methods

A. Research Procedures

This will be a non-randomized parallel group study in which a group of surgeons (Group A) will make determinations as to the material within each of four visually identical balloons that contain air, water, petroleum jelly or a firm substance similar to the consistency of a non-ripe banana (Figure 2) using their hands and eyes while another group of experienced robotic surgeons (Group B) will do so using the da Vinci Xi System (Intuitive Surgical, Sunnyvale, CA). Only Board-certified surgeons will be recruited for the study. The study information will be obtained at Valley Hospital and the Intuitive Surgical training facility in Atlanta, Georgia.

Surgeon demographics will be recorded on Case Report Form #1

Before making their “hands on” determinations as to balloon contents, each surgeon will be asked to first determine whether they can visually determine the balloon contents without any manipulation. For the purposes of outcome measurement, only two possible outcomes will be considered – namely that the 4 balloons were ordered correctly or not. We will also record each “guess” for all surgeons in order to report any trends of mis-assortment that may occur.

B. Duration for Study and Each Subject

Each study participant will spend about 5 minutes doing study activities. We estimate that we will be finished with data collection by September 1st, 2023

All data collection will be performed by [name]

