1.4 Sample Size Justification

The probability of ordering all balloons correctly by chance is 1/24 or .0417.

The expectation is that group A will achieve 100% success. If so, we will require **35 surgeons in Group A and 18 surgeons in Group B** to achieve 80% power to make the determination that Group B was (or was not) “non-inferior” at discerning balloons (alpha = 0.05).

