1.7 Data Collection

A. Primary Data Collection

- **Location:** The Valley Hospital and Intuitive Surgical Training Center in Atlanta GA. (Permission to conduct study at the Intuitive Surgical site obtained from [name] , Intuitive Surgical CMO.
- **Process of Data Collection:** Case Report Forms (see attached) will be filled out and collected by [name]
- **Timing and Frequency:** One time only per surgeon. Data collection will happen in 1 or 2 days at the Intuitive Surgical site – dates TBD
- **Procedures for Audio/Visual Recording:** N/A
- **Study Instruments:** The balloon model (Figure 2) is made of posterboard to which 4 balloons (Party City gold 5 inch) each containing 20 mL of material – either air, water, petroleum jelly, or water-absorbing crystals (LiquiLock, Oatey Inc) are affixed (Figure 1) The same model will be used for all data collection if possible, but in the event of balloon breakage or some other reason, identical replacement balloons may be created easily. The surgeons will be allowed to manipulate the balloons with their hands (Group A) or the robotic instruments (Group B) as they see fit, but they must leave the poster board laying flat with the balloons still attached. Surgeon Demographics (de-identified) and study data will be collected on Case Report forms 1 & 2. (Figures 3 & 4)
- **Ethnographic Studies, Interviews, Or Observation:** Surgeons will be allowed to manipulate the balloons as they see fit whether they are using their hands or the robotic instruments, but they will not be allowed to disconnect the balloons from the poster board. The poster board must lay flat at all times.

- **Subject Identifiers:** [name] will hold the key indicating which substance is in each balloon. Each surgeon will be assigned a subject number sequentially.

B. Secondary Data Collection

N/A

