5.4 Secondary Use of the Data

[figure not shown]
N/A

Figure 1.

Conventional laparoscopic surgery (which inherently includes haptic feedback to the surgeon) versus robotic-assisted surgery (which does not)

Laparoscopic surgery

- 1-4 small incisions for insertion of instruments
- Small, rigid instruments with specific motions
- Surgeon operates standing in a traditional operating room arrangement
- Surgeon views operative field on a video screen
- Requires specialized training to develop expertise

Robotic-assisted surgery

- 1-4 small incisions for insertion of instruments
- Small instruments with wide range of motion and tremor control
- Ability to operate in very tight or small spaces
- Surgeon operates seated inside a specially designed console to control robotic instruments
- Surgeon views 3-D image of operative field
- Requires substantial specialized training to develop expertise

Figure 2.

The balloons - each filled with 20 mL of either air, water, petroleum jelly or water absorbing crystals (consistency of a non-ripe banana)

[figure not shown]

Figure 3.
Case Report Form 1
Surgeon Demographics

Subject # _____

Board Certification (circle all that apply) FACS FACOG FPMRS
Other _____

Age _____

Male Female non-Binary

Years since residency _____

Years since fellowship _____

Credentialed for robotic surgery Y N

Approximate total number of robotic cases performed _____

Figure 4.

Case Report Form 2

Study Data Collection

Subject # _____

Surgeon felt as though they could discern balloon contents using only sight? Y N

Balloon discernment via manipulation

HANDS

ROBOT

AIR

WATER

JELLY

CRYSTALS

Correct? Y N

Y N

Y N

Y N

If No, which did they think it was?

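### Shredding the forms of surgeons who stop, and replacing them, can remove failures from the denominator without trace

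*Protocol*

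**What the plan says.** Section 4.4, Removing a Subject, gives the whole rule: "If a subject decides to cease participation we will shred their forms and choose a subsequent study subject". It names no stage of the session at which it ceases to apply and asks for no log of stops.

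Other provisions that bear on it:

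- **Order of events.** Under section 1.3 (Research Design and Methods), "each surgeon will be asked to first determine whether they can visually determine the balloon contents without any manipulation". Case Report Form 2 (Figure 4) records this as "Surgeon felt as though they could discern balloon contents using only sight? Y N". Manipulation and ordering follow.
- **Disclosure.** Section 4.4 (Subject Debriefing): "Each surgeon will be told whether or not they ordered the balloons correctly right after they do so".
- **Guesses.** Section 1.3 has each guess recorded "for all surgeons in order to report any trends of mis-assortment that may occur".
- **Numbering.** Section 1.7: "Each surgeon will be assigned a subject number sequentially".
- **Size.** Section 1.4 plans 35 surgeons in Group A and 18 in Group B, and section 4.3 gives the total as 53. Section 1.4 adds: "The expectation is that group A will achieve 100% success".

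**The concern.** The primary outcome is whether a surgeon ordered all four balloons correctly. A surgeon who finds the task hard and gives up is closer to a failure than to someone who was never enrolled, yet the rule treats the two alike: the record is destroyed and a new surgeon takes the place. If stopping is related to difficulty, the reported success rate is that of surgeons willing to finish, and the number who were not is lost.

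The direction is not neutral. If Group A performs at or near 100%, as planned, there are few failures there to lose. Losses would fall mainly in Group B and push the result towards the hypothesised non-inferiority. A stop in Group A alone works the other way.

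The loss is also permanent. Most choices about incomplete observations can be left to an analysis plan, but this one cannot, because the protocol itself orders the data destroyed.

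**Working it through.** **Step 1. What the rule removes, by stage of the stop**

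| Surgeon stops | Already on the forms | Effect of shredding |
|---|---|---|
| Before manipulation | Possibly demographics and the sight-only answer | No attempt lost |
| During manipulation, no guess made | Sight-only answer | An attempt that began is lost, with its group |
| After one or more guesses | Sight-only answer and guesses | Also removes guesses that section 1.3 says are recorded for all surgeons |
| After ordering, result disclosed | A complete primary outcome | Not expressly excluded by the rule |

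**Step 2. Can the rest of the record supply the missing count?**

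- The total cannot: replacement brings it back to 35 + 18 = 53.
- Sequential numbers could show gaps, but only if a number is not reused, and a gap reveals neither group nor result.
- In the form text available, group appears only as HANDS or ROBOT on Case Report Form 2, which is shredded. Form 1 asks about robotic credentials, but Group A requires only Board certification, so that item does not define group. Form 1 is among the shredded forms in any case.

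**Step 3. Size, as an illustration**

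The protocol gives no stopping rate, no non-inferiority margin and no sidedness for alpha = 0.05, so there is no stated figure to reproduce. Assumptions: a removed stop counts as a failure, and the planned group sizes are reached after replacement.

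Shift in the observed rate per removed failure when all completers are correct:

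- Group B: 1 - 18/19 = 5.3 points
- Group A: 1 - 35/36 = 2.8 points

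The lower bound for B minus A uses the Miettinen-Nurminen score method with variance factor N/(N-1). With Group A at 35/35, the constrained estimates at a deficit δ are 1 for A and 1 - δ for B. The bound is -δ, where δ is the larger root of

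(δ - d)² = z² · δ(1 - δ)/n_B · N/(N - 1),

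with d the observed deficit and z = 1.645 for one-sided 0.05.

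- 18/18: d = 0, N = 53. δ/(1 - δ) = 2.706 × 53/(52 × 18) = 0.153, so δ = 0.153/1.153 = 0.133.
- 18/19: d = 0.0526, N = 54. The factor is 2.706 × 54/(53 × 19) = 0.145. Solving 1.145δ² - 0.250δ + 0.0028 = 0 gives δ = 0.207.

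All cases, in percentage points:

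| Group B completers | One-sided alpha | Stop removed | Stop counted as failure |
|---|---|---|---|
| All correct | 0.05 | -13.3 (18/18) | -20.7 (18/19) |
| One wrong | 0.05 | -21.7 (17/18) | -27.5 (17/19) |
| All correct | 0.025 | -17.9 (18/18) | -24.9 (18/19) |
| One wrong | 0.025 | -26.0 (17/18) | -31.6 (17/19) |

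One removed Group B failure therefore improves the bound by 5.6 to 7.4 points. For a margin M, the verdict changes only if -M lies between the two bounds in a row.

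The opposite case is one stop in Group A only, counted as a failure (35/36 against 18/18). The bound is then -10.6 (0.05) or -15.3 (0.025), better for Group B than the -13.3 or -17.9 that would be reported. There the rule works against Group B.

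**The case against.** The strongest reply is that this is a withdrawal provision, not an analysis rule. Participation is a single session of about 5 minutes, and once the balloons are ordered nothing is left to cease. On that reading only unfinished attempts are shredded, and those have no primary outcome. Section 5.2 preserves case report forms, which fits. Consent is implied by participation, so a surgeon who stops can be taken to have withdrawn it. A forced ordering of four items always allows a guess, so a struggling surgeon need not quit. Nothing in the protocol points to difficulty-related stopping, and the bounds above assume that a stop is a failure, which is the point in dispute.

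Much of this stands. The natural reading probably excludes completed attempts, stops may be rare and harmless, and the figures are illustrations and do not estimate the bias. Destroying the forms of volunteers who withdraw is a defensible choice.

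Three points remain. The rule does not say that a completed ordering is safe, although the same section has the result disclosed immediately. An unfinished attempt that began is still informative about the task. And even if every stop is harmless, no one could show it afterwards, because no count by group is required. That count can be kept without identifiers, even if the forms are destroyed.

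**Conclusion.** The concern holds. The protocol fixes destruction and replacement with no cut-off and no count of stops by group, and a later analysis plan cannot undo this. That it biases the result is conditional: it requires at least some stops to be related to difficulty. The size is unknown, and the direction depends on the group in which the stops occur; the expectation of 100% in Group A makes Group B the likelier place. With only 18 surgeons in Group B, a single hidden failure is enough to move the lower bound by 5.6 to 7.4 points. Whether that alters the conclusion depends on a margin the protocol does not state. The change should be made before data collection; confidence is medium because the number of stops may turn out to be zero.

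**What to change.** Replace the rule in section 4.4 with the following:

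1. For every surgeon who begins manipulation, keep an anonymous record: subject number, group, timing of the stop and any guess made.
2. State the cut-off. An attempt is complete, and stays in the analysis, once the balloons have been ordered and before the result is disclosed. Surgeons who stop earlier may still be replaced.
3. Report non-completers by group and timing.
4. Add a sensitivity analysis that counts those who stopped after starting manipulation as not having ordered the balloons correctly.
5. State the retention on the Study Information Sheet, subject to ethics board agreement. If forms must be destroyed, keep at least an anonymous tally of stops by group and timing.

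The cost is a short protocol paragraph, one line on Case Report Form 2, one sentence on the information sheet and the ethics board's agreement. No identifiers are collected, so confidentiality is unaffected. The downside is that the sensitivity analysis will count an occasional stop unrelated to performance as a failure and may look slightly less favourable. For that reason it belongs beside the primary analysis and should not replace it.

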4.6 Risks and Benefits to Subjects

A. Description of Subject Risk And Benefits

There are no risks to being in this study. The benefits consist of the contribution each study subject will have made to further our knowledge of this topic.

Existing Condition/Disorder

N/A

- **Minimizing Risks**
N/A
- **Certificate of Confidentiality (CoC)**
N/A

- **Risks to Non-Subjects**
N/A
- **Potential Benefits**
The benefits consist of the contribution each study subject will have made to further our knowledge of this topic.

5.0 Data Management Plan

5.1 Data Analysis

Continuous variables will be compared via T-tests or Mann-Whitney test as applicable; Categorical data will be compared via chi square test. Power calculation / sample size estimate information as above.

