1.0 Research Design

1.1 Purpose/Specific Aims

A. Objectives

The objective of this study is to compare surgeons' discernment of 4 balloons filled with different materials when using their eyes and hands versus using the da Vinci robot.

B. Hypotheses / Research Question(s):

We believe that so called "visual haptics" derived from the high definition 3D optics associated with robotic surgery will allow for non-inferior object discernment compared to actual haptics of touching objects with surgeons' hands.

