1.6 Study Variables

A. Independent Variables, Interventions, or Predictor Variables

Primary outcome: (y/n) whether balloons were sorted correctly

Secondary outcome: Trends for any mis-assignments of balloons

De-identified surgeon demographics will be compared between groups

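### Non-inferiority is hypothesised and powered, but the only test named that fits the binary primary outcome is a chi-square test of difference, with no margin or decision rule

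*Protocol*

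**What the plan says.** - Section 1.1 B states the hypothesis: visual haptics "will allow for non-inferior object discernment compared to actual haptics of touching objects with surgeons' hands".
- Section 1.3 reduces each surgeon's result to whether "the 4 balloons were ordered correctly or not". Section 1.6 confirms it: "Primary outcome: (y/n) whether balloons were sorted correctly".
- Section 1.4 says "The expectation is that group A will achieve 100% success". On that basis it asks for 35 surgeons in Group A and 18 in Group B, to give 80% power for deciding whether Group B is non-inferior at alpha 0.05. It gives no margin, no expected Group B rate and no side for alpha.
- Section 5.1 assigns t-tests or Mann-Whitney tests to continuous variables. For the rest it says "Categorical data will be compared via chi square test", and then "Power calculation / sample size estimate information as above". The section it points back to contains no decision rule.

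**The concern.** A chi-square test asks whether two proportions differ. Non-inferiority asks whether B is worse than A by less than a stated amount. Rejecting equality does not settle that question, and failing to reject it with 18 surgeons in one group says little. The protocol does not claim that p > 0.05 means non-inferior, but it offers no other route from the data to the conclusion that it wants to draw.

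With no margin fixed in advance, the same data could be called non-inferior or not after the event. The power claim has the same gap, because power for non-inferiority has no meaning without a margin, a Group B rate and a test.

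The named test also suits the expected data badly. With Group A at 100%, failures can occur only in B and will be few, so expected cell counts are very small.

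**Working it through.** **Inputs.** From the protocol: n_A = 35, n_B = 18, Group A expected at 100%, power 80%, alpha 0.05. Assumed here: A observed at 35/35, and alpha one-sided unless stated otherwise.

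**1. Can 35/18 be reproduced?** The usual non-inferiority formula, with r = n_B/n_A, is

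n_A = (z_{1-α} + z_{0.80})² × [p_A(1-p_A) + p_B(1-p_B)/r] / (M - (p_A - p_B))².

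With p_A = p_B = 1 the variance is zero and the formula returns n = 0, so it does not give 35/18. Solved for the margin at p_A = 1, it reads M = (1-p_B) + (1.645 + 0.842) × √(p_B(1-p_B)/18). This gives 6.8, 17.8 or 27.6 points for a true B of 99%, 95% or 90%.

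Read instead as a pooled, uncorrected test of difference with ratio 35:18, two readings fit:
- 100% vs 80%, one-sided: 34.8 and 17.9.
- 100% vs 76%, two-sided: 35.1 and 18.0.

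Neither Group B rate is in the protocol, so the sample size does not reveal a margin.

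**2. What chi-square returns.** For f failures in B and none in A, the smallest expected count is 18f/53. At f = 1, Pearson X² = 53 × (35×1 - 0×17)² / (35×18×52×1) = 1.98, so p = 0.159.

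| B result | Smallest expected count | Pearson p | Fisher p | Yates p |
|---|---|---|---|---|
| 18/18 | 0 | undefined (0/0) | 1 | undefined |
| 17/18 | 0.34 | 0.159 | 0.340 | 0.732 |
| 16/18 | 0.68 | 0.044 | 0.111 | 0.212 |
| 15/18 | 1.02 | 0.013 | 0.035 | 0.063 |
| 14/18 | 1.36 | 0.004 | 0.010 | 0.019 |

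At 16/18 and 15/18, significance depends on which version of the test is used.

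**3. What the same data say about non-inferiority.** The Newcombe lower limit for B minus A is d - √[(p_B - l_B)² + (u_A - p_A)²], where l and u are Wilson limits. At 35/35, u_A = 1, so the limit reduces to l_B - 1. At 18/18, l_B = 18/(18 + 1.645²) = 0.869 and the limit is -13.1 points.

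| B result | Newcombe, one-sided 95% | Miettinen-Nurminen, one-sided 95% | Newcombe, 97.5% |
|---|---|---|---|
| 18/18 | -13.1 | -13.3 | -17.6 |
| 17/18 | -21.5 | -21.7 | -25.8 |
| 16/18 | -28.6 | -28.8 | -32.8 |

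At 17/18, B fails a 20-point margin and passes a 25-point one (one-sided 95%). The missing margin alone decides the verdict.

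**4. Illustration with M = 20 points (assumed).** By the confidence-limit rule only 18/18 passes, so the chance of success is p_B^18:
- 0.99^18 = 83%
- 0.98^18 = 70%
- 0.95^18 = 40%
- 0.90^18 = 15%

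Reaching 80% needs p_B ≥ 0.8^(1/18) = 98.8%. At a true B of 80%, the chance of a false claim is 0.80^18 = 1.8%.

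If p > 0.05 were read as non-inferior, that chance would be P(failures ≤ 1, 2, 3 of 18) = 9.9% with Pearson, 27% with Fisher and 50% with Yates, against a nominal 5%.

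**The case against.** Section 5.1 is generic and does not name the primary outcome. The only continuous variables in the protocol are demographics, so the sentence could be read as mainly a plan for comparing those. A separate SAP might hold the interval method, the handling of small cells and the decision rule. Each surgeon's result is recorded, so a confidence limit could be computed in any case.

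Part of this stands. The link from chi-square to the primary outcome is an inference, though a natural one, because the outcome is categorical and no other test for such data is named. The data would support a proper analysis. What is lacking is a criterion fixed beforehand. Small-cell handling alone would be a matter for the SAP.

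The core is not answered. The protocol makes a finished power claim for non-inferiority, which needs a margin and a Group B rate, and the test it names answers a different question. A later SAP would not make section 1.4 checkable or bring 5.1 into line with 1.1.

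The illustrative figures also have limits. They fix A at 35/35. With M = 20 and a true B of 95%, the chance of success is 40% on that basis, but 51% if true A is 99% and 59% if it is 98%. The 13-point floor depends on the method: treating A as known to be 100%, the exact one-sided limit at 18/18 is 1 - 0.05^(1/18) = 15.3 points below A.

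**Conclusion.** The concern holds and must be fixed, because it affects the study's only primary question. The analysis named in 5.1 cannot establish the hypothesis in 1.1, and the power in 1.4 is tied to no margin, Group B rate or non-inferiority test.

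With A at 35/35, a non-significant result at 17/18 still allows B to be about 21 points worse (about 26 if alpha is two-sided). Even perfect scores in both groups leave about 13 points (about 18 if two-sided). These limits rest on A at 35/35 and the Newcombe method, and Miettinen-Nurminen agrees within 0.3 points. Everything that uses 20 or 25 points is illustration, since the protocol gives no margin. The false-claim rates also assume a reading of p > 0.05 that the protocol does not state.

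**What to change.** **Section 5.1.** Keep chi-square for categorical demographics. For the primary outcome, substitute:

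> The one-sided 95% lower confidence limit for (success in B minus success in A) will be computed by the Newcombe method. Non-inferiority is concluded only if this limit lies above -M; otherwise the result is reported as non-inferiority not shown.

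Miettinen-Nurminen would serve equally, but one method must be chosen in advance. A Wald interval should not be used, because its width is zero at 35/35 vs 18/18.

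**Sections 1.1 and 1.4.** State M and justify it on substantive grounds before any data are seen. It should not be worked back from 35/18. With these numbers, no M below about 13 points can be met under the rule at 35/35 vs 18/18. In 1.4, also state whether alpha is one- or two-sided (if two-sided, use the 97.5% limit) and the assumed Group B rate, then recompute power for this rule.

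**Cost.** Wording in three sections, and probably a lower stated power. Group B may need to grow once M is set:
- M = 20, true B 95%, A at 35/35: 18 in B gives 40%. The smallest Group B reaching 80% is 28 (two failures allowed, 84%). The chance falls below 80% again at 31 to 34 because counts are discrete, so the final number needs an exact check.
- M = 25, same assumptions: 18 in B allows one failure and gives 77%.

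### Section 5.1 fixes chi-square for the binary primary outcome with no small-count exception, so at the failure counts the plan implies the result can depend on which chi-square is run

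*Protocol*

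**What the plan says.** Protocol section 5.1 (Data Analysis) gives one rule for each type of data. For continuous data it allows a choice: "Continuous variables will be compared via T-tests or Mann-Whitney test as applicable". For categorical data it does not: "Categorical data will be compared via chi square test". It does not say whether the continuity correction applies, and it names no exact test for sparse tables.

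The primary outcome falls under the categorical rule. Section 1.6 lists it as "Primary outcome: (y/n) whether balloons were sorted correctly", and section 1.3 (Research Design and Methods) reduces each surgeon's result to two values, "namely that the 4 balloons were ordered correctly or not".

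Section 1.4 states "The expectation is that group A will achieve 100% success" and sets the sample at "35 surgeons in Group A and 18 surgeons in Group B", with 80% power and alpha 0.05. It does not say whether alpha is one- or two-sided, and it gives neither a Group B success rate nor a non-inferiority margin. Section 1.1 hypothesises that the robotic view "will allow for non-inferior object discernment compared to actual haptics".

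**The concern.** Chi-square relies on a large-sample approximation that is doubtful when expected counts are small. Here the plan expects an empty failure cell in Group A, and its hypothesis implies few failures in Group B. Pearson's chi-square and the continuity-corrected version both go by the name in section 5.1. They differ most in sparse tables, so the same data could be reported as significant or not, with the choice open after the data are seen. The same rule covers the comparison of surgeon demographics in section 1.6, where some categories on Case Report Form 1 may also be small.

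**Working it through.** **Inputs.** From section 1.4: 35 in Group A, 18 in Group B, total 53; Group A expected at 100%; alpha 0.05. Assumed here: two-sided testing, and Group B success rates of 80% to 95% for illustration, because the protocol gives neither.

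**The plan's own figure.** The sample of 35 and 18 cannot be reproduced from section 1.4, which has no margin and no Group B rate. At 100% in both groups the usual non-inferiority formula has zero variance and returns 0. A difference test can be back-solved to about the stated size only by choosing a Group B rate: 80% one-sided uncorrected gives 35 in Group A, 75% two-sided uncorrected gives 34, and 73% one-sided with continuity correction gives 35. The stated 80% power therefore does not show which test was meant.

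**Expected counts.** With k failures in total, the expected number in Group B is k × 18/53:

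- k = 2: 0.68
- k = 3: 1.02
- k = 14: 4.75
- k = 15: 5.09

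The count reaches 5 only from k = 15. At k = 0 the failure column is empty and chi-square is undefined. The same arithmetic applies to a demographic category: if fewer than 15 surgeons fall in it, its expected Group B count is below 5.

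**p-values with Group A at 35/35.** With b failures in Group B:

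- Pearson: X² = 53 × (35b)² / [35 × 18 × b × (53 − b)]
- Corrected: replace 35b by 35b − 26.5
- Fisher: C(18, b) / C(53, b) for the counts shown

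For b = 2 the denominator is 35 × 18 × 2 × 51 = 64,260. Pearson is 53 × 70² / 64,260 = 4.04; corrected is 53 × 43.5² / 64,260 = 1.56; Fisher is 153/1,378 = 0.111.

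For b = 3 the denominator is 35 × 18 × 3 × 50 = 94,500. Pearson is 53 × 105² / 94,500 = 6.18; corrected is 53 × 78.5² / 94,500 = 3.46; Fisher is 816/23,426 = 0.035.

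| Group B failures | Pearson | Corrected | Fisher |
|---|---|---|---|
| 1 | 0.159 | 0.732 | 0.340 |
| 2 | 0.044 | 0.212 | 0.111 |
| 3 | 0.013 | 0.063 | 0.035 |
| 4 | 0.004 | 0.019 | 0.010 |

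The two chi-squares disagree at 2 and at 3 failures and agree at 1 and 4.

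**Sensitivity to the assumptions.** With one Group A failure, still two-sided, both versions are non-significant at 3 Group B failures (0.072 and 0.210), disagree at 4 (0.022 and 0.074) and are both significant at 5 (0.007 and 0.024). At one-sided 0.05 with Group A at 35/35, only 2 failures gives a disagreement (0.022 and 0.106); at 3 both are significant (0.006 and 0.031).

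**How often this would arise.** If Group A scores 35/35, the chance that Binomial(18, failure rate) equals 2 or 3 is 22%, 45%, 50% and 40% at assumed Group B success rates of 95%, 90%, 85% and 80%.

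**Power for an assumed 100% versus 80%, two-sided.** Group A contributes no failures, so power is the chance that Group B reaches the cut-off. Pearson rejects from 2 failures, Fisher from 3, corrected from 4. With a failure rate of 20% these chances are 90%, 73% and 50%.

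**Size.** Enumerating all 36 × 19 tables at common failure rates of 1% to 20%, the two-sided rejection rate is 1.0–4.6% for Pearson, 0.0–2.0% for the corrected test and 0.05–3.5% for Fisher.

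**The case against.** The choice between Pearson and the corrected version is ordinary SAP detail, and a SAP may exist. That is fair as to the variant alone. But the protocol does more than leave a detail open: it names chi-square for all categorical data without exception, while giving continuous data an alternative in the same section.

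A reader might infer that the type I error rate is badly wrong. The numbers do not support this. Pearson's overall two-sided size stays below 5% across the 1–20% range. At a common 5% failure rate it rejects 4.2% overall, with 4.1% in the direction of Group B being worse. That tail is close to its peak; it falls to 3.0% at a 10% failure rate and is below 2.5% at 1%. The 2.5% benchmark also presumes two-sided testing, which the protocol does not state.

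A reader might also infer that chi-square fails in every outcome the plan allows. The documents do not go that far. Only Group A has a stated expectation; few failures in Group B is an inference from the hypothesis in section 1.1. Fifteen or more Group B failures is not excluded, and section 1.4 itself puts success by chance at 1/24. The threshold of 5 is a rule of thumb.

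Finally, the verdict discussed here is that of a difference test, whereas the trial asks about non-inferiority. That is a separate and larger problem. It does not remove this one, because a large-sample interval for the difference would meet the same zero cell.

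**Conclusion.** The point holds in a limited form. Section 5.1 fixes an unsuitable and ambiguous test for the sparse table that section 1.4 leads one to expect. With Group A at 35/35 and two-sided 0.05, significance depends on the version of chi-square at 2 and at 3 Group B failures. Other assumptions move or narrow the disagreement, as shown above, but in the cases checked they do not remove it. For an assumed 100% versus 80%, power runs from 50% to 90% according to the test, so the stated 80% cannot be attached to chi-square as written. If nobody fails, which is the result most favourable to the hypothesis, the named test gives no answer. The finding rests on ambiguity and small expected counts, not on inflated type I error. It should be corrected before the data are analysed.

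**What to change.** In section 5.1, state that any categorical comparison with an expected count below 5, including any test of difference on the primary outcome, uses Fisher's exact test or one named unconditional exact test. With Fisher's test, two-sided, and Group A at 35/35, the cut falls at 3 Group B failures (p = 0.035), with no choice left to the analyst.

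For the non-inferiority question, report the Group B minus Group A difference in success with one named interval method that remains valid with a zero cell, preferably exact, and judge it against a prespecified margin. A Miettinen-Nurminen interval alone would not cure the sparse-table problem. At zero difference its statistic is Pearson's multiplied by (N − 1)/N: at 0 versus 2 failures that is 4.04 × 52/53 = 3.97, p = 0.046, the same verdict as Pearson.

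The cost is one or two sentences, with methods in standard software. The downside is that exact tests are somewhat conservative: Fisher's power in the 100% versus 80% example is 73%, below the 80% that section 1.4 claims.
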